## 9. STATISTICAL ANALYSIS

### 9.1 Sample size considerations

According to the available number of patients at our Department, including estimates of non-responders to a standard protocol of mRNA vaccination, and expected participation rates, we will attempt to include 60 patients into this trial. Based on a Chi test comparing 3rd mRNA versus vector vaccine, this number of patients will allow to achieve at least 80% power at a minimal detectable difference of 28% (5% of responders in the mRNA vaccine group versus 33% of responders in the vector vaccine group).

For differences smaller than the minimum detectable difference statistical significance will not be possible to claim.

### 9.2 Relevant protocol deviations

All protocol deviations will be listed in the study report. Major deviations regarding subjects' safety will lead to withdrawal.

### 9.3 Endpoints analysis

The primary endpoint (difference in SARS-CoV-2 antibody seroconversion rate by week 4 after vaccination boost at baseline between third mRNA SARS-CoV-2 (Biontech/Pfizer or Moderna) and vector SARS-CoV-2 vaccine (AstraZeneca)) will be analyzed using Chi-squared Test. For the seroconversion rates, 95% confidence intervals will be calculated. All subjects with available antibody responses fulfilling the eligibility criteria will be included in the analysis.

The secondary endpoints (see section 7.3.2) will be analyzed using descriptive statistics.

### 9.4 Missing, unused and spurious data

Only subjects for whom data are available will be included in the statistical analysis. Missing values will neither be replaced nor estimated.

### 9.5 Interim analysis

No interim analysis will be performed.

### 9.6 Software program(s)

Statistical analysis will be performed using R studios software or SPSS Statistics (Version 17.0 or higher).

## 12. DISCLOSURE OF DATA

The investigator will publish the results of the study as an original scientific report in a peer reviewed scientific journal. In addition, the findings will be presented as oral and poster presentations at international scientific meetings. All obtained data and information will be regarded confidentially.

No data, results or any information of this study may be used for publication without prior agreement of the principal investigator, who is mentioned on the title page of this protocol. The authors of a publication, manuscript, article, abstract or oral presentation, are those, who contribute to the results of the study and/or the writing of the paper. The principal investigator will write the first draft of the paper and – if applicable – delivers the related presentations. He will also be the first author of the main efficacy manuscript. The correspondence address mentioned in each publication is the Sponsor-investigator's address, as specified on the front-page. Additional co-authors will be determined based on their contributions during the course of the trial.

## 8. Study summary

**Background.** Treatment with rituximab (RTX), a monoclonal antibody targeting CD20, constitutes an important therapeutic strategy for patients with several chronic inflammatory conditions such as rheumatoid arthritis, systemic lupus erythematosus, mixed connective tissue diseases and neurological disorders like multiple sclerosis or immune-mediated peripheral neuropathies. Some recent reports have already highlighted the risk of serious consequences upon severe acute respiratory syndrome coronavirus 2 (SARS-CoV-2) infection in patients treated with RTX. Besides the risk of a more severe disease course during B cell depleting therapy, a major concern is the immunogenicity of vaccination during immunomodulatory therapies, especially with RTX. Indeed, RTX has been shown to impair humoral responses to various vaccines including SARS-CoV-2 vaccination. Studies from other vaccines have shown that an additional vaccination or a change of the vaccine can lead to development of a humoral immune response.

**Objective.** To investigate if a third vaccination with a vector based vaccine is superior to a further dose of the vaccine used for basis immunization in previous non responders receiving rituximab.

**Methods.** We will perform a prospective single blind randomized controlled study. A total of 68 patients under rituximab treatment will be enrolled in this clinical trial who received two vaccinations with an mRNA vaccine. Four study visits per patient will be planned. During the screening visit antibodies to the receptor-binding domain will be determined. All patients without detectable humoral immunity against SARS-Cov2 will be invited for a second boost vaccination within 4 weeks after the screening visit. During the baseline visit patients will be randomized to receive a third vaccination with either an mRNA-SARS-CoV-2 vaccine (Biontech/Pfizer or Moderna – according to the vaccine used for their first two vaccinations) or a vector SARS-CoV-2 (AstraZeneca) vaccination as a second boost. Additional study visits are scheduled at weeks 1 and 4 for assessment of humoral and cellular immunity, as well as clinical signs of adverse effects of disease activity reactivation. Patients without humoral response at week 4 will be offered participation in an extended follow-up for additional 8 weeks (i.e. at week 8 and 12 after baseline)

**Expected Results.** We expect at least 30% of patients receiving a third SARS-CoV-2 vaccination to develop humoral response after 4 weeks. The change in mode of action of the vaccine might be beneficial to induce response in patients with rituximab.

[97]

SARS-CoV-2 VAC3 study

EudraCT 2021-002348-57

Version 4.0, 10. August 2021

### 3. BACKGROUND

The current pandemic caused by severe acute respiratory syndrome coronavirus-2 (SARS-CoV-2) has led to exponentially rising morbidity and mortality worldwide. <https://coronavirus.jhu.edu/map.html>. Apart from aggressive quarantine and hygiene control measures, the most effective way to inhibit SARS-CoV-2 spread is a population-wide vaccination campaign. The SARS-CoV-2 pandemic has required rapid action and the development of vaccines in an unprecedented timeframe. Data from the preclinical development of vaccine candidates for SARS-CoV and MERS-CoV enabled the initial step of experimental vaccine design to be essentially omitted, saving a considerable amount of time. In many cases, production processes were adapted from existing vaccines or vaccine candidates, and in some instances, preclinical and toxicology data from related vaccines could be used. As a result, the first clinical trial of a vaccine candidate for SARS-CoV-2 began in March 2020. Trials were designed such that clinical phases are overlapping and trial starts are staggered, with initial phase I/II trials followed by rapid progression to phase III trials after an interim analysis of the phase I/II data.

More than 180 vaccine candidates, based on several different platforms, are currently in development against SARS-CoV-2. The World Health Organization (WHO) maintains a working document that includes most of the vaccines in development and is available at <https://www.who.int/publications/m/item/draft-landscape-of-covid-19-candidate-vaccines>.

RNA vaccines are a relatively recent development. The genetic information for the antigen is delivered instead of the antigen itself. The antigen is then expressed in the vaccinated individual cells. Either mRNA (with modifications) or a self-replicating RNA can be used. Higher doses are required for mRNA than for self-replicating RNA, and the RNA is usually delivered via lipid nanoparticles (LNPs).

Two mRNA vaccines, BNT162b2, developed by BioNTech/Fosun Pharma/Pfizer, and mRNA-1273 developed by Moderna/NIAID, are currently in phase III trials.

In December 2020, BNT162b2 was under evaluation for emergency use authorization (EUA) for widespread use by several medical regulators globally. On 21 December, the European Medicines Agency (EMA) has given official approval for the BNT162b2 vaccine developed by BioNTech and Pfizer.

SARS-CoV-2 VAC3 study

EudraCT 2021-002348-57

Version 4.0, 10. August 2021

On 18 December 2020, mRNA-1273 developed by Moderna/NIAID was issued an emergency use authorization by the United States Food and Drug Administration. On 06 January, the EMA has given official approval for the mRNA-1273, developed by Moderna/NIAID.

Preliminary results from Phase I–II clinical trials on BNT162b2, published in October 2020, indicated the potential for its efficacy and safety. Findings from studies conducted in the United States and Germany among healthy men and women showed that two 30- $\mu$ g doses of BNT162b2 elicited high SARS-CoV-2 neutralizing antibody titers and robust antigen-specific CD8+ and Th1-type CD4+ T-cell response. Besides, the reactogenicity profile of BNT162b2 represented mainly short-term local (i.e., injection site) and systemic responses. These findings supported the progression of BNT162b2 into the next phase. In phase III, a total of 43548 participants underwent randomization, of whom 43448 received injections: 21720 with BNT162b2 and 21728 with placebo. There were 8 cases of COVID-19 with onset at least 7 days after the second dose among participants assigned to receive BNT162b2 and 162 cases among those assigned to placebo. BNT162b2 was 95% effective in preventing COVID-19 (95% credible interval, 90.3 to 97.6). Similar vaccine efficacy (generally 90 to 100%) was observed across subgroups defined by age, sex, race, ethnicity, baseline body-mass index, and the presence of coexisting conditions.

In July 2020, preliminary results of the Phase I dose-escalation clinical trial of mRNA-1273 were published, showing dose-dependent induction of neutralizing antibodies against SARS-CoV-2 as early as 15 days post-injection. Mild to moderate adverse reactions, such as fever, fatigue, headache, myalgia, and pain at the injection site, were observed in all dose groups but were common with increased dosage. The vaccine in low doses was deemed safe and effective to advance a Phase III clinical trial using two 100- $\mu$ g doses administered 29 days apart.

In a Phase III trial of mRNA-1273 conducted in the United States between July and October, enrolled and assigned 30 000 volunteers to two groups — one group receiving two 100- $\mu$ g doses of mRNA-1273 vaccine and the other receiving a placebo of 0.9% sodium chloride. Preliminary data from Phase III clinical trial, published in November

SARS-CoV-2 VAC3 study

EudraCT 2021-002348-57

Version 4.0, 10. August 2021

2020, indicating 94% efficacy in preventing COVID-19 infection. Side effects included flu-like symptoms, such as pain at the injection site, fatigue, muscle pain, and headache. The Moderna results were not final – as the trial is not scheduled to conclude until late-2022– and were not peer-reviewed or published in a medical journal.

The efficacy of ChAdOx1 nCoV-19 vaccine was reported from phase III trials in the United Kingdom and Brazil. The interpretation of the results of these trials is complicated by a dosing error (in which some participants unintentionally received a half-dose for their first of two doses), a small number of participants, and differences in efficacy in the two countries. The overall efficacy in preventing symptomatic infection more than 14 days after the second dose was 70.4% (95%CI: 54.8%-80.6%), with efficacy of 62.1% (95%CI: 41.0%-75.7%) in those who received standard doses, and 90.0% (95%CI 67.4% to 97.0%) in those who received a half-dose followed by a standard dose. Notably, the lower efficacy was based on results from the study in Brazil, and higher efficacy was reported for the study in the United Kingdom. Hospitalizations and severe COVID-19 occurred rarely but exclusively in the placebo arm of these trials. Due to varying intervals between the first and second doses, vaccine efficacy after a single standard dose from day 22 to day 90 was modeled and estimated to be 76% (95%CI: 59%-86%), with maintenance of antibody levels up to day 90. Furthermore, vaccine efficacy appeared to be 82.4% (95%CI: 62.7%-91.7%) when the interval between doses was more than 12 weeks compared to 54.9% (95%CI: 32.7%-69.7%) when the interval was less than 6 weeks. Similarly, geometric mean antibody levels were higher with a longer prime-boost interval in those age 18-55 years. A larger phase III trial using two standard doses 28 days apart with a majority of the participants in the US recently completed enrollment. Preliminary results of this trial showed vaccine efficacy of 76% (95%CI: 68-82%) at preventing symptomatic infection and 100% efficacy at preventing severe or critical disease and hospitalization. Vaccine efficacy was consistent across ethnicity and age. TheChAdOx1nCoV-19 vaccine has received EUA from the United Kingdom and the European Union. In the United Kingdom, a single-blind multi-center randomized phase II/III trial of the ChAdOx1 nCOV-19 vaccine asked participants to provide a weekly self-administered nose and throat swab starting one week after administration of the first vaccine (or placebo). This study revealed that among those who were infected,

[101]

SARS-CoV-2 VAC3 study

EudraCT 2021-002348-57

Version 4.0, 10. August 2021

vaccinated persons had lower peak viral load and shorter duration of RT-PCR-positive results for SARS-CoV-2 compared to controls, suggesting that the vaccine is effective in reducing transmission.

Patients with immunosuppression with COVID-19 may be at higher risk of hospitalization and ICU admission than matched comparators. An mRNA vaccine vaccination should be performed as primary immunization with two vaccine-doses 21 or 28 days apart. There are no data about the efficacy and safety of mRNA vaccine against SARS-CoV-2 in patients with a chronic immune-mediated disease such as rheumatoid arthritis, certain kinds of vasculitis, lupus multiple sclerosis. However, after vaccination, immune responses might vary among immunosuppressed patients, dependent upon underlying clinical conditions and the level of immunosuppression. Moreover, it is not clear whether mRNA vaccination against SARS-CoV-2 in the immunosuppressed has a protective effect at all. Specifically, B-cell depleting therapies like CD20 antagonists rituximab have a high risk of vaccination failure. As for other vaccines, the efficacy of a COVID-19 vaccine may be reduced in patients treated with rituximab. For patients treated with rituximab, it is preferable to administer the vaccine at least 6 months after the last infusion to have the highest possible number of restored B-cells. The current treatment scheme for rituximab is 500mg or 1000mg intravenously every 6 months.

However, the vaccine is not contraindicated in this population and the treating physician should discuss with the patient the appropriate timing of vaccination taking into consideration the context of pandemic, the risk of poor COVID-19 disease prognosis, and a possibly reduced humoral response to vaccination under rituximab treatment.

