### 6.2. Inclusion criteria

Male and female subjects will be eligible for participation in this study if they:

SARS-CoV-2 VAC3 study

EudraCT 2021-002348-57

Version 4.0, 10. August 2021

22. Are  $\geq 18$  years on the day of screening
23. Have a chronic condition and have been treated with a B-cell depleting therapy (rituximab) within the last 12 months
24. Received two doses of mRNA SARS-CoV-2 (Biontech/Pfizer or Moderna) vaccine according to recommendations in the label and/or national guidelines.
25. Did not develop humoral immunity 4 weeks after second mRNA vaccination to SARS-CoV-2 (analyzed during the study “Characterization of immune responsiveness after mRNA SARS-CoV-2 Vaccination in patients with immunodeficiency or immunosuppressive therapy”, EK-Nr. 1073/2021, EudraCT Nr. 2021-000291-11)
26. A maximum of 6 months after second vaccination
27. Have an understanding of the study, agree to its provisions, and give written informed consent before study entry
28. If female and capable of bearing children – have a negative urine pregnancy test result at study entry and agree to employ adequate birth control measures for the duration of the study

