## 9. STATISTICAL ANALYSIS

### 9.1 Sample size considerations

According to the available number of patients at our Department, including estimates of non-responders to a standard protocol of mRNA vaccination, and expected participation rates, we will attempt to include 68 patients into this trial. Based on a Chi test comparing 3rd mRNA versus vector vaccine, this number of patients will allow to achieve at least 80% power at a minimal detectable difference of 28% (5% of responders in the mRNA vaccine group versus 33% of responders in the vector vaccine group).

For differences smaller than the minimum detectable difference statistical significance will not be possible to claim.

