### 9.3 Endpoints analysis

[124]

SARS-CoV-2 VAC3 study

EudraCT 2021-002348-57

Version 4.0, 10. August 2021

The primary endpoint (difference in SARS-CoV-2 antibody seroconversion rate by week 4 after vaccination boost at baseline between third mRNA SARS-CoV-2 (Biontech/Pfizer or Moderna) and vector SARS-CoV-2 vaccine (AstraZeneca)) will be analyzed using Chi-squared Test. For the seroconversion rates, 95% confidence intervals will be calculated. All subjects with available antibody responses fulfilling the eligibility criteria will be included in the analysis.

The secondary endpoints (see section 7.3.2) will be analyzed using descriptive statistics.

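### The primary chi-squared test uses neither the B-cell randomisation stratum nor time since rituximab: a modest loss of efficiency that is cheap to avoid

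*Supplement*

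**What the plan says.** All references are to protocol V4.0; its section 9 is the analysis plan.

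- Section 3 (Background): for patients on rituximab, "it is preferable to administer the vaccine at least 6 months after the last infusion". The sentence goes on to give the reason, which is to have as many B cells restored as possible. The treatment cycle is given as 6 months.
- Section 6.2, criterion 23: patients qualify if they "have been treated with a B-cell depleting therapy (rituximab) within the last 12 months". No minimum interval is set.
- Section 6.5: allocation is 1:1, stratified by B-cell depletion (yes/no) as found at screening.
- Section 7.3.2: seroconversion by B-cell repopulation is a secondary endpoint, which section 9.3 treats descriptively.
- Section 9.1: "we will attempt to include 68 patients into this trial", and "this number of patients will allow to achieve at least 80% power at a minimal detectable difference of 28" percentage points, from "5% of responders in the mRNA vaccine group versus 33% of responders in the vector vaccine group".
- Section 9.3: the primary endpoint "will be analyzed using Chi-squared Test". No stratum or covariate is mentioned. "For the seroconversion rates, 95% confidence intervals will be calculated".

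**The concern.** The protocol gives its own reason to expect response to vary with B-cell recovery, and with the time that recovery takes. It acts on this at randomisation through a two-level stratum. The primary test then compares raw proportions. Variation in response that B-cell status or infusion timing could explain stays in the comparison as noise.

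Both variables are fixed before randomisation. The stratum is recorded by design, and the infusion date is needed to check criterion 23. The yes/no stratum cannot carry the graded information within each half, because patients may enter at any point up to 12 months after treatment.

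With 34 patients per arm and few responders expected, the stakes are some power and a less precise estimate of the difference between vaccines.

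**Working it through.** **Inputs.** From the documents: 68 patients at 1:1, so n = 34 per arm; response rates 5% and 33%; a non-directional alternative (section 5.1). Section 9 states no alpha, so two-sided 0.05 is assumed, in line with the 95% intervals. Not in the documents, and assumed: the prognostic strength of B-cell status and of infusion timing.

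**1. The plan's own power.** With p0 = 0.05, p1 = 0.33 and mean 0.19:

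z = [0.28·√34 − 1.96·√(2·0.19·0.81)] / √(0.05·0.95 + 0.33·0.67) = (1.633 − 1.087) / 0.518 = 1.05, so power = 85.4%.

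Exact enumeration gives 89.0% for the uncorrected chi-squared test and 81% with Yates' correction or Fisher's test. The claim of at least 80% reproduces under each.

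**2. Expected responders.** At 5% versus 33%: 34 × 0.05 = 1.7 and 34 × 0.33 = 11.2, about 13 in all. At 20% versus 50%: 6.8 + 17 = 23.8, about 24. The second scenario is not the protocol's planning case. It is included because the study summary expects at least 30% of third-dose recipients to respond: 5% and 33% average 19%, while 20% and 50% average 35%.

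**3. Power at 20% versus 50%.** Simulation with 34 per arm, stratum log-odds 2, 50% or 70% B-cell depleted, and 4,000 trials per cell (standard error about √(0.8·0.2/4000) = 0.6 points):

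| Timing log-odds per SD | 0 | 0.5 | 1.0 | 1.5 |
|---|---|---|---|---|
| Unadjusted chi-squared | 78% | 79–80% | 78–79% | 78% |
| Stratified by B-cell depletion | 83–84% | 83–84% | 82% | 81% |
| Stratum plus timing | 82–83% | 85% | 87% | 90% |

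Stratifying gains about 3 to 5 points. A further run with 60% depleted put the extra gain from timing at about 0 / 1 / 5–6 / 10 points.

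**4. Power at 5% versus 33%.** The planned test already has about 90% in these simulations. Stratifying adds about 1 to 2 points, and timing a further 0 / 1 / 3 / 4. At 1.0 log-odds per SD, for example, adding timing moves the stratified test from 90.6% to 93.5%.

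**5. Cross-check under a different model.** Time was taken as uniform over 0–12 months, about 34% not depleted, and allocation balanced within stratum. An odds ratio of 7.4 per 6 months equals ln(7.4) × (12/√12)/6 = 2.0 × 3.46/6 = 1.15 log-odds per SD. Adding time alone moved power from 89.8% to 92.9%. Where response depended only on B-cell status, stratifying moved power from 90.5% to 92.8% (odds ratio 10) and from 91.7% to 95.6% (odds ratio 30).

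**6. Type I error.** The unadjusted test stayed at about 5% or below. It fell to 1.1–3.3% when B-cell status was strongly prognostic (odds ratio 10 to 30), where the stratified test held 4.7–4.9%. The score test adjusted for timing ran at 4.6–6.6%, which is why a permutation p-value is needed.

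**7. Sparse data.** At a 5% rate the mRNA arm has no responder with probability 0.95^34 = 17.5%, and at most one with probability 0.175 + 34 × 0.05 × 0.95^33 = 49%. With none, ordinary logistic regression has no finite estimate of the vaccine effect.

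**The case against.** The strongest reply is that the design already deals with the mechanism. The Background names restored B cells as the aim and time only as the route to them, and section 6.5 balances the arms on measured B-cell depletion. Nothing in the documents says that weeks since infusion predict response once B-cell status is known. At the protocol's own rates the gain is a few points on a test that already has enough power, and with about 13 responders a covariate model is fragile.

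Most of this stands. It limits the size of the point and calls for a sparse-data fallback. It does not explain why the stratum chosen for randomisation is missing from the primary test.

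Three stronger readings are tempting, and the documents do not support them.

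- That the protocol makes time since infusion the factor deciding response. It does not: section 3 also mentions underlying conditions and the level of immunosuppression.
- That chance imbalance in timing undermines the result. Randomisation protects the type I error. Any imbalance figure worked out as if allocation were unstratified would also overstate the risk. With stratification, the cross-check model gave a gap of 15 points or more in the share at least 6 months from rituximab in about 10% of trials.
- That the 12-month window contradicts the Background. The Background states a preference, says that vaccination is not contraindicated, and leaves timing to physician and patient. The point here concerns the analysis only.

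**Conclusion.** The point holds as a modest loss of efficiency. The primary test ignores both its own randomisation stratum and a baseline date that the eligibility check already requires.

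Assuming a B-cell log-odds of 2, using the stratum is worth about 1 to 2 points of power at 5% versus 33% and 3 to 5 at 20% versus 50%. Timing is worth a further 0 to 4 and 0 to 10 points over an assumed 0 to 1.5 log-odds per SD, with essentially no loss if it is not prognostic. The upper ends need both strong prognostic effects and response rates above those in section 9.1.

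The planned test is valid, if conservative when B-cell status matters, and the stated power is met as it is. The change is worth making because it is cheap, not because the trial would otherwise fail.

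**What to change.** Amend section 9.3 before unblinded data are analysed:

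1. Stratify the primary analysis by B-cell depletion as used at randomisation, with weeks from last rituximab infusion to vaccination as the only additional covariate.
2. Take the p-value from permuting arm within stratum. Report a standardised risk difference with 95% CI.
3. Prespecify penalised (Firth) logistic regression, or a fallback to the Mantel-Haenszel stratified risk difference and test, if an arm has no or very few responders. Fix the threshold in advance.
4. Keep the unadjusted chi-squared test as a sensitivity analysis.

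If the sponsor judges the responder count too small for the covariate in the primary model, the minimum change is a B-cell-stratified primary test with infusion timing as a prespecified sensitivity covariate.

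The cost is a few lines in 9.3, one derived variable (after confirming that the exact infusion date is recorded) and a short permutation script. No extra patients, visits or samples are needed.
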